**N. Does this project involve international research?  YES  NO**

1. *For further instructions refer to [VHA Directive 2005-050](#), Requirements for Conducting VA-Approved International Research Involving Human Subjects, Human Biological Specimens, or Human Data*
2. *VHA Handbook 1200.05 definition of international research - VA international research is any VA-approved research conducted at international sites (not within the United States (U.S.), its territories, or Commonwealths); any VA-approved research using either human biological specimens (identified, de-identified, or coded) or human data (identified, de-identified, or coded) originating from international sites; or any VA-approved research sending such specimens or data out of the U.S. (see par. 56). **NOTE:** For the purposes of this Handbook, research conducted at U.S. military bases, ships, or embassies is not considered international research.*

**O. Study Procedure**

1. **Study Procedures**

Outline all study procedures - (If necessary, include a table or flow chart, showing the schedule of the procedures and interactions. Distinguish between interventions that are experimental and carried out for research purposes vs. those that are considered

standard of care. Routine procedures that are performed solely for research purposes should also be identified.) **Recruitment for this study will happen in a few ways. For the majority of our potential participants, we will be using pharmacy records and reaching out by letter and phone call (Letter and phone script provided).** We will use VA pharmacy records to identify Veterans who are currently being prescribed daily opioid medication for the treatment of chronic pain. Veterans already in treatment for alcohol use disorders (AUD) will then be excluded from the study. Veterans in treatment for opioid use disorders who are on a daily medication assisted regimen (i.e. OTP program) will be included as long as they have a chronic pain diagnosis and no AUD. For potentially eligible patients, we will send an encrypted email to the prescribing physicians (See email content below). If a PCP objects to our intent to recruit their patient, we will not send that Veteran a letter. If the clinician does not object to the study team contacting the potential subject we will contact potential subjects via letter to describe the research study and follow-up with a telephone call to invite them to participate (phone script provided). We respect the time of all the Veterans we are recruiting for this study. We want to ask these other questions because if we can clearly determine a Veteran is not eligible, we do not want to make them come in for a long consent/screening/baseline appointment and then be told they cannot participate. The Veteran may have to pay to take public transportation to the VAMC, or may be upset after completing the long first session and finding out they cannot participate. We want to limit unnecessary costs and agitation experienced by Veterans we are recruiting.

There are a few potential outcomes of the screening call:

- If they are not eligible for the study and the Participant will not be contacted again. No referral or communication of results will be made. If they are ineligible due to screening positive for a substance use disorder (by having 5 or more symptoms on the exclusion checklist), then they are drinking (or using) at too high a level and the results of this screening will be communicated to BHL for further clinical care.
- If they are not currently receiving mental health services at the MHC, and eligible: If Veteran decides to participate, a study counselor will complete the Brief Intervention only after participant has been consented to participate in the study and admits to any drinking. If the counselor determines their alcohol use is severe enough to necessitate more intensive treatment (i.e. inpatient treatment), the Veteran will be referred to the higher level of care and will be removed from our study. If Veteran decides not to participate, the technician will thank them for their time and end the call. A research note describing the outcome of screening call will be created in CPRS.
- If they are currently receiving mental health services at the MHC, and eligible: If Veteran decides to participate, a study counselor will complete the Brief Intervention only after participant has been consented to participate in the study. If Veteran decides not to participate or is later found to be ineligible, standard care through the MHC will continue as if he/she had never been contacted about the study. A research note describing the outcome of screening call will be created in CPRS.
- If they are not currently receiving mental health services at the MHC, and ineligible: A research note describing the outcome of screening call will be created in CPRS.
- If they are currently receiving mental health services at the MHC, and ineligible: Standard care will continue through the MHC as if the Veteran had never been referred to the study. A research note describing the outcome of screening call will be created in CPRS.

- It is possible through the course of receiving care at the CMCVAMC that a Veteran has received a BI in the past. However, this treatment could have occurred far enough in the past (i.e. greater than 3 months) that the BI would need to be repeated. As we cannot ensure a Veteran has received a recent (within the past 3 months) BI through the MHC, the study staff will perform the BI's for those Veterans.
- If enrolled in the Opiate Treatment Program and eligible: If Veteran decides to participate, a study counselor will complete the Brief Intervention only after participant has been consented to participate in the study. If Veteran decides not to participate or is later found to be ineligible, standard care through the OTP will continue as if he/she had never been contacted about the study. A research note describing the outcome of screening call will be created in CPRS.
- If enrolled in the Opiate Treatment Program and ineligible: Standard care will continue through the OTP as if the Veteran had never been referred to the study. A research note describing the outcome of screening call will be created in CPRS.

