For those who are potentially eligible following the phone screen (and interested in participating), the next step is coming to the VA for consent. After consent, subjects will complete the first research visit. Final eligibility is determined after consent using the SCID and MINI. If after learning more about the study during the consenting process, the Veteran decides not to consent, or if they are ineligible following the SCID and MINI, then the Veteran will continue to receive services at the CMCVAMC to which they are eligible and entitled to. This could include services through the BHL or MHC. Similarly, Veterans can also elect to stop their participation in the study and can withdraw without penalty in writing using the revocation form at any time after they have consented to the study. In this case, their normal care at the CMCVAMC will continue.

Veterans who meet criteria for participation will be randomly assigned to either receive the usual care (that which they would have gotten if they had not chosen to be in the study); or Prevention Intervention (PI).

As a result of relaxing our inclusion criteria, it is likely that we will randomize Veterans who have not consumed alcohol in the past three months. For those Veterans, we will monitor their alcohol use during the research follow up visits at 3, 6, and 9 months. If they report having a drink of alcohol, we will then begin which treatment arm they had been randomized to. If the Veteran does not report taking a drink prior to the 9 month follow up, they will simply continue with the 12 and 18 month follow ups but will never have the Brief Intervention or Prevention Intervention.

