drinking to below risky levels. In addition to sending tailored messages as described above, the SMS system will conduct on average weekly ecological assessments. (Ecological assessments are research questionnaires that happen in the “real world.” Ours will entail text messages such as: “Have you met the goal you set for yourself over the past week? Please respond 1 (not at all), 2 (somewhat) or 3 (mostly).” These are different from the motivational messages and are used to track progress and inform phone counseling sessions.) Veterans who are having trouble meeting their goals will receive more assessment messages. Veterans who initially reduce alcohol use to safe levels and are therefore placed in the monitoring track will transfer over to the more intensive prevention track if their alcohol use increases to risky levels at some point in the 12-month intervention. Veterans whose alcohol or drug use escalates to DSM-V moderate to severe substance use disorder levels will be given a referral to specialty care and their progress will be evaluated at regular follow-up visits.

Although the research counselors will be able to alter the messaging frequency and scripts based on the progress of the Veteran, decision support rules based on change will help guide messaging content and frequency to reduce research counselor burden. The system will alert research counselors to reductions in motivation or other red flags that may indicate the Veteran needs more support and will include proactive “help messages” for Veterans in the moment, which will trigger just-in-time messages and system alerts. In addition, Veterans can decide on the minimum and maximum number of messages they wish to receive per week. The text message conversations between our research counselors and the study participant will also be recorded and kept in an encrypted database.

All participants will be using their own cell phones during their participation in the study. We will instruct participants to inform us if they lose/damage their phone. However, we will not replace Veterans’ personal cell phones. If data security is breached, we will follow VA and HIPAA mandatory disclosure procedures. If data is lost but not breached (e.g. to server malfunction), we will assess the situation and alert the study sponsor.

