10.6. Will informed consent be obtained from potential subjects prior to determining eligibility?

YES  NO  N/A

10.6.1. If no, provide justification and a HIPAA Waiver of Individual Authorization for Disclosure of Protected Health Information. **We will be using pharmacy**

records to identify Veterans who are prescribed opioids for chronic pain. This will be done prior to obtaining consent. Potential participants will answer screening questions prior to consent. This is a tool used in the clinics that we will use as an initial screening tool. The results of the screening will be coded to safeguard each Veteran's PII/PHI. A spreadsheet located on our secured study drive will be used to pair Veteran data to the code. Potentially eligible participants who then sign a consent form will undergo more in-depth screening to determine eligibility for randomization.

- 10.7. Define when a subject is enrolled into the study, e.g. after the subject signs the informed consent or after randomized to treatment. **A subject is enrolled once they have been randomized.**
- 10.8. Describe:
  - 10.8.1. The process when informed consent will be obtained and protecting patients' privacy. **Consent will be obtained at the first research visit.**
  - 10.8.2. Any waiting period between informing the prospective participant and obtaining consent. **The Veteran will be told of the study via letter. After the letter is sent potential subjects will receive a telephone call. However, obtaining consent will not occur until after the Veteran completes the VA's standard alcohol assessment and some other screening questions over the phone.**
  - 10.8.3. Steps taken to minimize the possibility of coercion or undue influence. **Veterans will be explained clearly as to what is standard of care and what is research. They will be reminded over and over that research is voluntary. The consent will be reviewed at each research follow up visit as consenting is a process and not a one-time event.**
- 10.9. Provide the language
  - 10.9.1. used by those obtaining consent **The language suggested by the VA consent template will be used.**
  - 10.9.2. understood by the prospective participant or the legally authorized representative **It is assumed that the reading level understood by the population is 8th grade as that is considered the average reading level understood by Americans.**
- 10.10. Provide location where informed consent will be obtained. **MIRECC interview rooms.**

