e. Missing values. The mixed effects models will provide valid estimates of treatment efficacy if the missing data meet the ignorable missingness assumption. We will conduct further analyses to assess the sensitivity of our inferences to possible violations of this assumption. First, we will use pattern mixture models (104), defining a categorical variable describing the main patterns of missing data, and including it as a main effect and interaction effect with intervention group in the modes for primary outcomes. Significant differences in the estimated intervention effects across levels of the pattern variable suggest one type of non-ignorable missingness. Second, shared parameter models (104) assume that the repeated responses and repeated binary indicators of missingness have possibly correlated random effects, and significant correlation indicates possible non-ignorability. Finally, semiparametric regression models (106) use inverse probability weighting to extend the validity of GEE models, and provide a different type of sensitivity analysis for the mixed effects models. All three approaches require certain model assumptions, so we will compare the results of the analyses over a range of such assumptions.

X. **Privacy and Confidentiality** (*Privacy refers to persons and to their interest in controlling the access of others to themselves.) (Confidentiality refers to protecting information from unauthorized disclosure or intelligible interception.) (Investigator should contact the Privacy Officer for additional details.)*

1. **Indicate the type of data that will be received by the Principal Investigator. Check all that apply.**

- 1.1.  De-identified – Without any identifiers that could link the data to a specific participant. (Contact Privacy Officer for assistance. If data is coded, it is not considered de-identified.)
- 1.2.  Identified – Linked to a specific participant by identifiers sufficient to identify participants. (See [HIPAA](#) and [Common Rule](#) Criteria for list of identifiers.)
- 1.3.  Coded – Linked to a specific subject by a code rather than a direct identifier. If coded is checked, specify:

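### Removing a Veteran from the study for severe drinking found at the brief intervention can fall after randomisation and lose outcomes tied to the endpoint; outcome collection should continue after referral.

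*Combined protocol and SAP*

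**What the plan says.** Among the outcomes of the screening call in section O.1, the bullet for eligible Veterans not receiving MHC services says that a study counselor gives the BI "only after participant has been consented to participate in the study and admits to any drinking". It then sets a condition: "If the counselor determines their alcohol use is severe enough to necessitate more intensive treatment (i.e. inpatient treatment"; if that is met, "the Veteran will be referred to the higher level of care and will be removed from our study". The bullets for MHC patients, Opiate Treatment Program patients and referrals from the Behavioral Health Lab (BHL) contain no such rule.

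Three other places bear on what happens next.
- Under Prevention Intervention Group, PI Veterans whose use rises to a moderate to severe disorder "will be given a referral to specialty care and their progress will be evaluated at regular follow-up visits".
- Under Study visits, every participant is seen at each research follow-up: months 3, 6, 9, 12 and 18, or to month 12 only for those enrolled after 4/1/2019.
- Section W.4.2.e rests the primary analysis on a condition: "The mixed effects models will provide valid estimates of treatment efficacy if the missing data meet the ignorable missingness assumption". It then plans pattern mixture, shared parameter and inverse probability weighted sensitivity analyses.

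No section says whether a removed Veteran goes on attending research visits, how that Veteran's outcome is scored, or which participants make up the primary analysis set. Intention-to-treat is not mentioned.

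**The concern.** The primary outcome is risky drinking in each follow-up window. A rule that ends participation because drinking is severe selects on something close to that outcome. If it acts after randomisation, the participants lost are not a random subset, and the loss arises from the protocol rather than from chance dropout. Both arms' risky-drinking rates would then be understated. If the rule is used more readily in one arm than the other, the between-arm comparison is biased as well. Baseline drinking is not a listed covariate in the primary model (W.4.2.a), so the model does not condition on the most obvious predictor of removal, and ignorability is doubtful for these Veterans.

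**Working it through.** **Does removal fall after randomisation?**
- Section R.10.7: "A subject is enrolled once they have been randomized".
- The Brief Intervention Only (BIO) arm is the BI itself; the PI arm is the BI plus text messages and calls. The BI is therefore part of what is allocated.
- Veterans with no recent drinking are randomised first. When they report a drink, "we will then begin which treatment arm they had been randomized to"; if they report none before month 9 they "will never have the Brief Intervention or Prevention Intervention". For this group the order is certain.
- For baseline drinkers, the Brief Intervention (BI) paragraph says only that both groups have had the BI or will be scheduled for it. Post-randomisation timing is strongly implied but not explicit.

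**What is lost?** A baseline non-drinker who first reports drinking at month 3, 6 or 9 already has at least one outcome window, which a mixed model would use; the later windows go. A baseline drinker removed before month 3 has no outcome window at all. So the complete loss occurs in the group where the timing is implied, and the partial loss in the group where it is certain.

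**Do the passages conflict?** The section O.1 rule concerns inpatient-level need found at the BI in non-MHC Veterans of either arm. The PI passage concerns later escalation to a moderate to severe disorder. Triggers and timing differ, so both can operate. They meet in a non-MHC PI Veteran whose BI is delayed until drinking is reported: one passage ends participation, the other continues follow-up.

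**The plan's own sample size (W.4.1, March 2018).** The formula for one measurement is n per arm = [1.96√(2p̄q̄) + 0.8416√(p₁q₁ + p₂q₂)]² / (p₁ − p₂)². It is multiplied by (1 + 4ρ)/5 for five windows and divided by the fraction retained.
- 35% vs 20%: 137.9 per arm. At ρ = 0.3 and 0.4 this becomes 60.7 and 71.7. Divided by 0.9, it gives 68 and 80 per arm, or 136 and 160 in total (stated 136 to 162).
- 35% vs 15%: 72.4 per arm, giving 36 and 42 per arm, or 72 and 84 in total (stated 72 to 84).

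The figures reproduce. The 10% loss and the pairing with ρ of 0.3 to 0.4 are assumptions, because the amendment states neither.

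**Illustration of removal.** Inputs from the protocol are the 35% and 20% rates, ρ of 0.3 to 0.5, alpha of 5%, five windows, and 150 treated Veterans. Assumptions are a 1:1 split (75 per arm), every removed Veteran a risky drinker with no follow-up data, and the 20% dropout of W.4.1 accruing linearly. Mean loss is then 20% × (3+6+9+12+18)/(5×18) = 10.7%, so retention is 0.893. The documents give no removal count, so a range is shown.

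*Equal removal, 5 per arm, true rates 35% vs 20%.* BIO: (26.25 − 5)/70 = 30.4%. PI: (15 − 5)/70 = 14.3%. The difference moves from 15.0 to 16.1 points and the odds ratio from 2.15 to 2.62. With no true effect both arms move together and type I error stays at 5%.

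*Unequal removal, no true effect, 35% in both arms.* With x removed from one arm only, its rate is (26.25 − x)/(75 − x). Each arm's effective size is n × 5 × 0.893/(1 + 4ρ). The rejection probability is Φ(t − 1.96) + Φ(−t − 1.96), where t is the artefact divided by its standard error.

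| Excess removals | Observed rate | Artefact (points) | Type I error, ρ 0.5 to 0.3 |
|---|---|---|---|
| 1 | 25.25/74 = 34.1% | 0.9 | 5.2 to 5.3% |
| 2 | 24.25/73 = 33.2% | 1.8 | 5.9 to 6.2% |
| 5 | 21.25/70 = 30.4% | 4.6 | 11.3 to 13.6% |

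Worked case, x = 5, ρ = 0.4: standard error 0.0594, t = 0.0464/0.0594 = 0.78, rejection 12.3%. For x = 5, counting only false positives that favour the depleted arm, with a pooled null variance, gives 10.8 to 13.2%.

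**The case against.** The strongest reply has four parts.

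1. **The trigger is narrow.** It is inpatient-level need, not heavy drinking. Veterans with five or more symptoms on the phone checklist, or a moderate to severe disorder at the SCID/MINI step, are already excluded. The rule appears in one bullet only. This stands, and it makes small numbers likely. It does not make them zero: the March 2018 amendment deliberately enrols Veterans thought to under-report drinking, so severity may first surface at the BI.

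2. **Both arms receive the BI and the rule names no arm.** This stands: equal removal leaves the null test valid. It still shifts the rates and the odds ratio.

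3. **Non-ignorable sensitivity analyses are planned.** This stands as a credit to the plan. None is tied to these removals, and no model recovers outcomes for a Veteran with no follow-up data.

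4. **The two passages do not directly contradict each other.** Correct. They overlap in one kind of case, and neither settles data collection after removal.

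A reader might go further and infer that the plan deletes the heaviest drinkers' data, or that unblinded counselors decide who leaves. The documents support neither. Nothing says collected data are discarded. Counselors do deliver both the BI and the PI calls, but whether they know the allocation when giving the BI is not stated.

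**Conclusion.** The point holds as a gap in the plan that is cheap to close. As written, the rule can end outcome collection after randomisation for a reason tied to the endpoint, and no all-randomised analysis set covers those Veterans. Likely damage is modest: one or two excess removals in an arm move the comparison by 0.9 to 1.8 points and type I error to about 5 to 6%. Reading the 5-versus-0 case (4.6 points, about 11 to 14%) as the expected effect would go too far; it is an assumed upper illustration. All these sizes rest on the assumed removal counts, on every removed Veteran being a risky drinker without follow-up data, and on 75 per arm with five windows, although Veterans enrolled after 4/1/2019 have four. Whether the order of BI and randomisation exposes baseline drinkers to complete loss depends on a point the protocol leaves unclear.

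**What to change.** - Reconcile the removal rule in section O.1 with the Prevention Intervention Group and Study visits text, and state for baseline drinkers whether the BI comes before or after randomisation.
- Leave the referral, and any stopping of study treatment, to the investigators. State that referral after randomisation does not end research outcome collection unless the Veteran withdraws consent.
- In W.4.2, define the primary analysis set as all randomised Veterans in their assigned arm.
- Report referrals and removals by arm and by time since randomisation. If any Veterans still leave with no outcome, say how they enter the W.4.2.e sensitivity analyses.

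The cost is protocol wording, plus continued research visits, already scheduled, for what is probably a handful of Veterans. Some of them may be hard to reach while in more intensive treatment.
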